Investigate association between post-intervention EEG improvement and SzNET response. The estimand of interest is the relative risk of EEG improvement in patients with more than 50% improvement of their SzNET by TVR and PSI.

3.4. Aim 4

Investigate the association between the post-intervention typical resting state networks (RSN) connectivity improvement and the SzNET response. The estimand of interest is the relative risk of improvement of the RSNs in the patients with more than 50% of improvement of their SzNET by TVR and PSI.

3.5. Aim 5

Describe psychosocial functional measure outcomes and ambulatory ASM toxicity at 3 months from hospital discharge. The estimates of interest will be the PROMIS Emotional Distress—Anxiety— Short Form, the Neurological Disorders Depression Inventory for Epilepsy (NNDI-E), the QOLIE-10-P, the Telephonic Montreal Cognitive Assessment, and the Liverpool adverse event profile test. All will be assessed at the 3 month follow up visit by one of the NSICU Post-Discharge clinics. This aim only applies to the patients that are discharged alive from the hospital and will include results from visits until 14 months after the enrollment start.

3.6. Aim 6

Assess the trial's design feasibility success in enrollment and retention for our actual institutional context by evaluating the enrollment rate and dropout rate among participants at the end of the trial. It will be composed by two sub aims.

Aim 6a

Measure the participants enrollment rate during the hole study enrolling months. The estimand of interest will be the rate of enrolled patients per month.

Aim 6b

Measure the participants dropout rate among participants. The estimand of interest will be the dropout rate from the total enrolled participants at the end of the study.

4. Study Design

This is a prospective interventional, uncontrolled, open-label, single center pilot study in moderate to severe acute brain injury (MSABI) patients with suppression of consciousness. The study main outcomes require pre and post-intervention rs-fMRI data collection to characterize the evolution of SzNET, a physiological measure of brain function. Clinical implementation of rs-fMRI is still novel, not frequently performed at early stages of MSABI, and has few medical indications as a follow-up test. As this data is infrequently generated during the standard of care (SOC), a prospective interventional study with an ASM intervention and a research funded rs-fMRIs is needed.

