These variables will be collected as part of the safety monitoring. Some of these variables also aim to determine how practical and viable is the study design, recruitment strategies, and participant retention in our institutional actual context. By closely monitoring the enrollment rate, which measures the efficiency of the recruitment process, and the dropout rate, which indicates the probability of the participants to continue with the study. Valuable insights can be gained regarding the feasibility of conducting a similar study on a larger scale. This findings will provide crucial information for refining future study protocol and improving recruitment and retention strategies to ensure the successful implementation of future research projects with similar conditions.

5. Study Participants

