5.1. Numbers of Participants

5.1.1. Number to be screened: N=68

5.1.2. Number to be enrolled: N = 54

Rationale of Number Expected to be Screened:

The Study will employ a quota sampling method to enroll four groups of patients, designated as: SzNET+/EEG+, SzNET+/EEG-, SzNET-/EEG+, and SzNET-/EEG-. Importantly, only the two SzNET+ groups have a minimum enrollment goal. Thus, enrollment will stop once each of the two SzNET+ groups enroll ten patients. The logic behind the patient screening and enrollments is as below.

1. SzNET+/EEG- Strata: To successfully complete the study treatment in 10 EEG- subjects, who would eventually be found to be SzNET+, we need to enroll 11 subjects, as we anticipate a 1 in 10 subject attrition. In our preliminary SABI data (Fig 2), of those who would meet inclusion/exclusion criteria, 30% with EEG- were SzNET+. Thus, we expect to need to enroll approximately 37 EEG- patients with completed good quality studies. Lastly, due to the ICU environment and the Barthel score required, we expect 80% of the subjects eligible for enrollment, thus 46 EEG- patients will be screened to fulfill this group's recruitment goal.

2. SzNET+/EEG+ Strata: To successfully complete treatment in 10 EEG+ subjects, who would eventually be found to be SzNET+, we need to enroll 11 patients, as we anticipate a 1 in 10 subject attrition. In our preliminary SABI data (Fig 2), of those who would meet inclusion/exclusion criteria, 67% of the EEG+ were SzNET+. Thus, we expect to need to enroll approximately 17 EEG+ patients with completed good studies. Lastly, due to the ICU environment and the Barthel score required, we expect 80% of the subjects eligible for enrollment. Thus, 22 EEG+ patients will be screened to fulfill this group's recruitment goal.

Participants who drop out, are withdrawn, or have missing data will not be replaced until second aim's data is complete, afterwards we will continue recruitment until we meet the two strata proposed enrollment. The subjects analyzed for the second aim will only include those scanned until the time when the first group of SzNET+/EEG+ or SzNET+/EEG- recruitment will be completed. By this strategy, the initial estimate of the proportion of SzNET+ subjects by EEG subgroup could be less biased, and we will guarantee the required number of subjects to start the interventional phase of the study while optimizing the total amount of initial rs-fMRI needed.

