Sources of recruitment: UNCH PICU, NSICU, SICU, CTICU, CICU or MICU patients meeting study inclusion and exclusion criteria. Potential research subjects will be identified by the study team members chart screening of all the patients with EEG orders from ICU, for eligibility.

Interventional Study numbers of enrollees expected to receive the treatment regimen: Since this is a non-controlled interventional open-label pilot study, and we need a total of 20 subjects successfully to receive the study therapy AND repeat rs-fMRI, then due to intra-study attrition of 1:10, we expect to treat a total of 22 patients with the study therapy.

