 - ◆ Rs-fMRI does not require contrast agents to be administered.
 - ◆ In case of tattoos with suspected high levels of ferromagnetic compounds cold compresses can be applied to prevent heating.
 - ◆ Transportation through the hospital to perform the MRI scan can be associated with mechanical risks and support devices malfunction. Trained personnel is in charge of the process, which is supervised by a physician.

○ SzNET Stratification of rs-fMRI

- SzNET (-): with EEG (+) or EEG (-).
 - ◆ N=32
 - ◆ No protocol Intervention-driven, combined ASM is administered.
 - ◆ They will not receive the second fMRI.
 - ◆ They will only be followed at the 3 months post discharge visit if they are scheduled to one of the NSICU Post-Discharge clinics.
 - ◆ MRI scan transportation related AE Review.
- SzNET(+): with EEG(+).
 - ◆ N=11
 - ◆ Proceed with combined ASM Intervention.
 - ◆ Intervention **must** start within 1 to 6 days after enrollment.
 - ◆ AE Review.
- SzNET(+):with EEG(-)
 - ◆ N=11
 - ◆ Proceed with combined ASM Intervention.
 - ◆ Intervention **must** start within 1 to 6 days after enrollment.
 - ◆ AE Review.

○ Study team will inform the family of the rs-fMRI results and upload the official report to EPIC.

Intervention start (Days 1-6 from Enrollment)

- **Clinical Care Team** will choose the intervention regimen.
 - If participant was already on **two** of the protocol-approved ASM, the participant will be required to start the intervention by administering the protocol-driven loading dose infusions outlined for

each of the combined ASMs, or by administering the loading dose for any of the other 5 listed ASM options. A third option in this case is to administer protocol-driven loading dose of one of the current medications and add another of the 5 ASM loading dose and maintenance regimen.

- If participant was already on **one** of the protocol-approved ASM, the participant will be required to start the intervention by administering the protocol-driven loading dose outlined for the ASM that the participant was previously receiving *along with* another protocol-driven ASM loading dose from the ones listed on the protocol.
- If participant **was not receiving any** of the protocol approved ASM, the participant will be administered a loading dose of two of the 5 protocol approved ASM.
- If the clinical care team does not want to use a combination of two of the 5 protocol-approved ASMs, they will not be enrolled into the study.

- **Research Team** will

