7.8. Early Discontinuations

Data to be Collected The care team may adjust the treatment plan of all patients to ensure optimal medical management, including the study intervention. Patients who do not meet the treatment criteria (which requires treatment with two of the ASM regimens specified in the protocol for at least 72h from loading dose) or who are unable to undergo the rs-fMRI#2 after completing the minimum intervention time and within 72 hours of their last dose of the intervention protocol will be considered dropouts. For these patients, only the clinical data available at the time of enrollment and their initial rs-fMRI data will be collected for analysis of aim #2. However, this data cannot be used for other outcomes analysis. Nonetheless, we will still collect information about the reason for dropping out and any reported adverse events.

Subjects missing follow-up after rs-fMRI#2 and repeat EEG are performed will have all the study data already collected except for the data asked at one of the NSICU Post-Discharge clinics for exploratory outcomes.

Criteria for Intervention Discontinuation

- Changes in the medical condition that contraindicate the use of at least two of the medications mentioned in the valid intervention list.
- Developing a medical condition that does not allow the rs-fMRI#2 scan.
- Presenting a grade 4 AE.
- Presenting a grade 2 to 3 AE without adequate measures to solve the event and prevent its study-related recurrence.

Requiring more aggressive ASM treatment because of seizures worsening or the need to change one ASM from the protocol list for another listed ASM is allowed.

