Measure the enrollment during all the months of study enrollment. The primary outcome of interest is the rate of monthly enrolled patients.

Aim 6b

Measure the participants dropout among participants during the study. The primary outcome of interest is the dropout rate among the total number of enrolled participants at the end of the study.

We will calculate the summary statistics of these measurements.

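### Aim 6b plans one dropout rate over all enrolled, but treatment-phase dropout can occur only in SzNET+ patients, so at planned counts it is diluted about 2.5-fold

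*Combined protocol and SAP*

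**What the plan says.** Aim 6b has the same denominator in both places where it is defined. Section 3.6: "The estimand of interest will be the dropout rate from the total enrolled participants at the end of the study". Section 8.3: "The primary outcome of interest is the dropout rate among the total number of enrolled participants at the end of the study", followed only by a commitment to summary statistics.

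Section 7.8 says who counts as a dropout: patients who do not receive two protocol ASM regimens for at least 72 hours from the loading dose, or who cannot have rs-fMRI#2 after the minimum intervention time and "within 72 hours of their last dose of the intervention protocol will be considered dropouts". Their initial scan is kept for Aim 2, so they have already been scanned.

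SzNET- patients receive no study treatment (sections 4.2 and 6), and section 6 adds: "They will not receive the second fMRI". Section 6 plans 32 of them.

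Section 5.1 places the attrition assumption in the treated group: "we need a total of 20 subjects successfully to receive the study therapy AND repeat rs-fMRI", and "due to intra-study attrition of 1:10, we expect to treat a total of 22 patients with the study therapy".

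Section 4.3 gives the purpose of the measure: "the dropout rate, which indicates the probability of the participants to continue with the study". It adds that the findings will inform a similar study on a larger scale. Sections 2.1 and 4.2 describe that study as a trial in EEG-/SzNET+ patients.

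**The concern.** The numerator and denominator do not match. The events that section 7.8 calls dropout arise only after a patient has been found SzNET+ and allocated to treatment. The denominator is everyone enrolled, most of whom are planned to be SzNET- and cannot have such an event. A rate built this way understates treatment-phase attrition and cannot be set against the 1-in-10 assumption that produced the 22.

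The definition is also not settled. Table 2 in section 4.3 records dropout at any time after enrollment, and section 7.9 allows withdrawal at any time, whereas section 7.8 lists treatment-phase events only. If losses before allocation also count, one number pools two losses with different causes and different implications.

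What is at stake is the planning of the follow-on trial. Its planners need the share of SzNET+ patients who do not reach rs-fMRI#2, particularly in the EEG- stratum, and separately the share lost before the first scan result. The planned summary gives neither.

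**Working it through.** **Inputs.** Planned enrolled 54 (section 5.1). Planned SzNET+ 22, as 11 per EEG stratum (sections 5.1 and 5.5). Planned SzNET- 32 (section 6). SzNET+ share 30% in EEG- and 67% in EEG+ (section 5.1). Preliminary data: 27 of 63 SzNET+ (section 2.1). Suspension trigger: five allocated patients who do not complete the intervention and follow-up tests (section 12.5).

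**Step 1: reproduce the plan's counts.**
- EEG-: 11/0.30 = 36.7, rounded up to 37.
- EEG+: 11/0.67 = 16.4, rounded up to 17.
- Enrolled: 37 + 17 = 54, as stated.
- Treated: 20 × 1.1 = 22, as stated.
- SzNET-: 54 − 22 = 32, as stated.

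**Step 2: dilution of a treatment-phase event.** For x events, the ratio of the two rates is (x/SzNET+) ÷ (x/enrolled) = enrolled/SzNET+, whatever x is.
- Planned counts: 54/22 = 2.45.
- Expected yield: 37 × 0.30 + 17 × 0.67 = 22.49, and 54/22.49 = 2.40.
- Preliminary share: 63/27 = 2.33.

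**Step 3: what would be reported with no other losses** (exact Clopper-Pearson 95% intervals).

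| Treatment-phase non-completers | Over 22 SzNET+ | Over 54 enrolled |
|---|---|---|
| 2 (planned attrition) | 9.1% (1.1 to 29.2) | 3.7% (0.5 to 12.7) |
| 5 (suspension trigger) | 22.7% (7.8 to 45.4) | 9.3% (3.1 to 20.3) |

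**Step 4: what would be reported if earlier losses also count.** Hold treatment-phase dropout at 2 and add k losses before allocation. The rate is (2 + k)/54.

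| k | 0 | 1 | 2 | 3 | 4 |
|---|---|---|---|---|---|
| Rate | 3.7% | 5.6% | 7.4% | 9.3% | 11.1% |

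Treatment-phase retention is the same in every column, but the reported figure triples.

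**Step 5: precision of the SzNET+ rate.** With 22 patients, the exact interval for any count from 0 to 5 includes 10%. The first count whose interval excludes it is 6: 27.3% (10.7 to 50.2). In one stratum, 1/11 = 9.1% (0.2 to 41.3).

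**The case against.** The strongest reply is that the denominator fits the aim. Aim 6 concerns enrollment and retention of participants, and any enrollee can be lost: by voluntary withdrawal (section 7.9), by recovery before therapy (section 2.2), or by brain death or a serious event (section 12.2). Nothing in section 3.6 or 8.3 limits Aim 6b to section 7.8 events. A follow-on trial would also have to enroll and scan patients to find those who are SzNET+, so all-enrolled retention is useful to it. On this view the 2.45 describes a quantity that Aim 6b does not claim to report.

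Much of this stands. The all-enrolled rate is a valid overall retention measure and should stay. The 2.45 applies to the treatment-phase component alone. But if every loss counts, the pooling in step 4 takes the place of the dilution, and the plan still does not say which losses count.

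Two further points are fair. The data are collected and section 12.5 already counts allocated non-completers, so a reader given the right counts could do the division. Feasibility is a stated aim, though, and its retention measure is better fixed before the counts are known. The illustrations are also limited. The five-patient trigger is cumulative and could be reached before 22 are allocated or 54 enrolled. Aim 6b has no threshold, and the 1-in-10 figure belongs to the treated group, so an all-enrolled rate above or below 10% decides nothing.

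**Conclusion.** The point holds as a minor gap in the planned summary; data collection is adequate. At planned counts, treatment-phase dropout is diluted 2.45-fold when divided by all enrolled, or 2.33 to 2.45 across the SzNET+ shares the protocol itself supplies. The planned 9.1% would appear as 3.7%.

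This rests on two assumptions: that the planned 22 and 54 are realised, and that no other losses are counted. Actual counts may differ, since after Aim 2 is complete "we will continue recruitment until we meet the two strata proposed enrollment". If other losses are counted, the problem becomes one of mixing, and the single rate can fall below or above the treatment-phase rate.

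**What to change.** In sections 3.6 and 8.3, keep the all-enrolled dropout rate, state which losses it counts, and add two pre-specified rates:

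1. Among participants SzNET+ on rs-fMRI#1, the proportion who do not complete the minimum intervention and rs-fMRI#2 for any reason. This includes voluntary withdrawal and recovery before therapy, and excludes losses after rs-fMRI#2. Report it overall and by EEG stratum, with exact 95% intervals and causes.
2. Among all enrolled, the proportion lost before the rs-fMRI#1 result.

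Show rate 1 beside the assumed 1 in 10 as a description, not a test, because 22 patients cannot support a test.

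The cost is SAP wording and a few table rows. Dropout, its date and cause, EEG status and SzNET status are already recorded per patient (section 4.3, Table 2), and no study procedure changes. The drawback is that rate 1 will look less favourable than the all-enrolled rate when losses are mainly in the treatment phase, and its interval will be wide, especially by stratum.

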8.4. Planned Interim Analyses

No interim analyses will be performed.

9. Sample Size Rationale

There is no preliminary data for effect size estimation using the paradigm and patient population suggested in this study. In Aim 1, a paired t-test is used to test measurement differences before and after ASM. A effect size 0.806 can be detected for a 1-sided test at a power of 80% and a Type I error at 0.05 with the total of 11 subjects before and after ASM. In Aim 4, a transformed Z-test is used to test correlation between two variables. A correlation size 0.506 can be detected for a 1-sided test at a power of 80% and a Type I error at 0.05 with the total of 22 subjects.

10. Data Capture and Database Management

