8.1. Strategies that Apply to all the Aims

All statistical procedures will be performed in SAS and R. Biostatistician [name] will oversee all data analyses.

- (i) All data will be scored and rescored by separate staff members and checked for accuracy prior to double entry into our database. All datasets are backed up daily.

- (ii) Prior to statistical modeling, we will perform descriptive analyses and data visualizations to examine the distributions of all measures. Appropriate transformations to obtain approximate normality will be performed; where necessary, additional nonparametric tests will confirm results.
- (iii) Linear regression model and nonparametric tests (e.g., Wilcoxon rank sum test) will be the primary analytic tools for testing our *a priori* hypotheses. Model selection methods (e.g., Bayesian information criterion) and sensitivity analysis methods will be used to select models and assess various model assumptions. We will consider the use of appropriate covariates as detailed below in all aims.
- (iv) We will record the reasons for drop-outs, missing / censored data values, and protocol departures in the database. We will appropriately handle drop-outs and missing data (e.g., missing responses and/or covariates) by using imputation or other estimation methods (e.g., missing completely at random), while considering anticipated causes. We will carry out sensitivity analysis to evaluate different missing mechanisms.
- (v) We will use test statistics (e.g., likelihood ratio test) to test the hypotheses. To identify significant component terms in each of the models, we will examine the parameter estimates, 95% confidence intervals, and p-values of the component terms in an analysis of fixed effects for the final regression models. All statistical estimates of population parameters will be tabulated along with corresponding confidence intervals (CIs) and/or standard errors (SEs) to convey levels of precision / imprecision.

We will use graphical methods such as forest plots to visualize the analysis results. We will also include outcome-dependent exploratory analyses to generate new hypotheses.

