Investigate association between post-intervention EEG improvement and SzNET response. The outcome of interest is the relative risk of EEG improvement in patients with more than 50% improvement of their SzNET by TVR and PSI.

H_0 : there will be no difference in the EEG improvement between the patients with and without more than 50% improvement of their SzNET.

H_1 : EEG improvement will be greater in the patients with more than 50% of SzNET improvement.

There are 22 subjects used in Aim 3. We will fit logistic regression model to characterize the association between the EEG improvement with the patients with and without more than 50% improvement of either PSI or TVR. We will use the Wald test and likelihood ratio test statistics to test the null and alternative hypotheses.

Plans for Aim 4.

Investigate association between the post-intervention typical resting state networks (RSN) connectivity improvement and the SzNET response. The outcome of interest is the relative risk of improvement of the typical RSN in the patients with more than 50% of improvement of their SzNET by TVR and PSI.

H_0 : there will be no difference in the typical resting state networks connectivity improvement between the patient with and without more than 50% improvement of their SzNET.

H_1 : Median typical resting state networks connectivity improvement will be greater in the patients with more than 50% of SzNET improvement.

There are 22 subjects used in Aim 4. We will fit logistic regression model to correlate the RSN improvement with the patients with and without more than 50% improvement of either PSI or TVR and use the Wald test and likelihood ratio statistics to test the null and alternative hypotheses.

Plans for Aim 5.

Describe psychosocial functional measure outcomes and ambulatory ASM toxicity at 3 months from discharge. The outcomes of interest will be the PROMIS Emotional Distress—Anxiety— Short Form, the Neurological Disorders Depression Inventory for Epilepsy (NNDI-E), the QOLIE-10-P, the Telephonic Montreal Cognitive Assessment, and the Liverpool adverse event profile test. All will be assessed at the 3 month follow-up visit to one of the NSICU Post-Discharge clinics.

Plans for Aim 6.

Aim 6 is to assess the trial's design feasibility success in enrollment and retention by evaluating the enrollment rate and dropout rate among participants at the end of the trial.

Aim 6a

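### Section 9's Aim 4 power figure is for a correlation test that Section 8.3 does not plan, and Aims 3 and 4 list Wald and likelihood ratio tests with no lead, although Wald cannot reject when a cell is empty

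*Combined protocol and SAP*

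**What the plan says.** - Section 9, on power: "In Aim 4, a transformed Z-test is used to test correlation between two variables". It continues: "A correlation size 0.506 can be detected for a 1-sided test at a power of 80" percent, with type I error 0.05 and 22 subjects. It gives no figure for Aim 3.
- Section 8.3, Aim 4: "We will fit logistic regression model to correlate the RSN improvement" with an indicator of more than 50% SzNET improvement. "There are 22 subjects used in Aim 4"; Aim 3 also uses 22. Section 4.3 defines both EEG improvement and RSN improvement as binary.
- Section 8.3, Aim 3, on testing: "We will use the Wald test and likelihood ratio test statistics to test the null and alternative hypotheses". Aim 4 names the same pair. The general rule in Section 8.1(v) gives the likelihood ratio test only as an example: "We will use test statistics (e.g., likelihood ratio test) to test the hypotheses".
- On estimation, Aim 3 states: "The outcome of interest is the relative risk of EEG improvement in patients with more than 50% improvement"; Aim 4 has the same form. Section 8.1(v) adds: "All statistical estimates of population parameters will be tabulated along with corresponding confidence intervals" and/or standard errors. Neither section says how the relative risk or its interval will be computed.
- On numbers, Section 5.1 expects to treat 22 so that 20 receive therapy and a repeat scan. Section 7.8 limits dropouts' data to Aim 2.

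**The concern.** A power statement should describe the test that will be run on the patients who will be analysed. Here the test in Section 9 and the analysis in Section 8.3 are different procedures, and the number analysed is open.

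Listing two tests without a lead also matters at this sample size. If every responder improves, or no non-responder does, the logistic slope has no finite estimate and its standard error becomes very large. The Wald statistic then goes to zero, while the likelihood ratio statistic stays finite. One table can therefore give a clear rejection by one listed test and none by the other, and the plan does not say which is reported. At stake are clear reporting of Aims 3 and 4 and what the follow-on trial takes from them.

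**Working it through.** **1. Section 9's figure.** Inputs from Section 9: r = 0.506, N = 22, one-sided 0.05. Power by Fisher's z is Φ(atanh(r)·√(N−3) − 1.645).
- atanh(0.506) = 0.5573 and √19 = 4.359, so Φ(2.429 − 1.645) = 78.4%. With the bias term r/(2(N−1)) = 0.0120 added to atanh(r), it is 79.9%. The stated 80% reproduces.
- The same test at N = 20 has 74.3% (76.1% with the bias term).

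**2. The number analysed.**
- Towards 20: Section 5.1 (22 treated, 1 in 10 lost, 20 completing) and Section 7.8 (no dropout data outside Aim 2).
- Towards 22: Section 5.1 on continuing recruitment to the planned strata, Section 8.1(iv) on imputation, and the Aim 1 plan in Section 8.3 (22 with before and after measurements).
- Towards fewer: Section 5.1 also stops enrolment at ten per SzNET+ group. At its attrition that is 20 × 0.9 = 18 completers, and Section 9's own test then has 70–72% power.

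**3. Power of the planned 2x2 analysis.** The documents give no response split or improvement rate. Assume an even split, 50% improvement overall and phi = 0.506, since the correlation between two binary variables is phi. The risk difference is then 0.506 × 0.5/0.5 = 0.506, so the risks are 0.5 ± 0.253, or 75.3% v 24.7%. Enumerating all tables, one-sided 5%, with Wald counted as not rejecting when a cell is empty:

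| Test | N = 22 (11/11) | N = 20 (10/10) |
|---|---|---|
| Likelihood ratio | 85% | 80% |
| Wald | 76% | 68% |
| Fisher exact | 71% | 63% |

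**4. How often a cell is empty.** Under the same assumptions at 10/10: 0.753^10 + 0.247^10 = 0.059 per group, so 1 − (1 − 0.059)² = 11% of samples. At 11/11 it is 9%. With a 14/6 split and 50–80% improving overall (also assumed), it is 18–49%.

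**5. One table, N = 20.** Responders 10/10 improved, non-responders 6/10.
- Likelihood ratio: maximised log-likelihoods are 0 and −6.730 by group, and −10.008 pooled. G = 2(−6.730 + 10.008) = 6.556 and √G = 2.560, so one-sided p = 0.005.
- Wald: standard error about 15,200 (it depends on the software's convergence tolerance). One-sided p is about 0.50 (two-sided 0.999).
- Fisher exact: one-sided p = 0.043. Boschloo: one-sided p = 0.021.
- Relative risk 1.00/0.60 = 1.67; risk difference 0.40.

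**6. Type I error of the likelihood ratio test.** By enumeration, the one-sided 5% test has a maximum size of about 5–8% at common improvement rates of 50–70%. It reaches 8–12% only at extreme rates.

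**The case against.** The best defence is that little is lost. Phi is a correlation, and at phi = 0.506 the likelihood ratio test has 80–85% power with an even split, so Section 9's 80% is about right for one of the two listed tests. This stands, and it limits the harm. It does not make a correlation test the planned analysis, and it does not cover the Wald test or Aim 3.

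Section 8.1 also leaves room: (ii) allows additional nonparametric tests where necessary, (iii) allows sensitivity analyses, and (v) promises estimates with intervals and/or standard errors. The Statement of Compliance follows guidance against relying on a significance threshold. An analyst facing an empty cell could therefore reach for an exact test, but no clause names one or says which result leads.

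A reader might infer more than the documents support:
- That 0.506 is miscalculated. It is not.
- That 22 is the wrong number. Sections 5.1, 8.1(iv) and 8.3 can be read to keep it; it is unreconciled, not shown to be wrong.
- That the two tests point in opposite directions. Both come from the same fit with the same sign; with an empty cell Wald is merely uninformative.
- That empty cells will be common because Section 2.1 reports SzNET improvement in all six treated pilot patients. That improvement is not defined by the 0.5 TVR/PSI rule, and Section 9 says there are no preliminary data for effect size in this setting.
- That the likelihood ratio test is badly inflated. At improvement rates of 50–70% the excess over 5% is at most about 3 points.

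**Conclusion.** The concern holds as a minor point. Section 9's Aim 4 figure is correct for a test that Section 8.3 does not plan, Aim 3 has no figure, and the number analysed is unsettled between 22 and 20, or 18 on one reading. At N = 20 the two listed tests differ by 12 points of power (80% v 68%), and they can lead to different conclusions on one table.

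The 2x2 power figures rest on an assumed phi of 0.506, an even split and 50% improvement. The failure of the Wald test with an empty cell rests on none of these. Section 4.3 lists EEG and RSN improvement as secondary outcomes of this pilot, and no trial decision depends on their p-values. The consequence is confined to reporting and to planning the next trial.

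**What to change.** **Section 8.3, Aims 3 and 4.** Drop the Wald test. Name one lead test, one-sided at 5% to match the directional alternatives and Section 9, that copes with empty cells: for example Boschloo or Fisher exact, or a penalised (Firth) likelihood ratio test if covariates are used. Report the relative risk and risk difference with score or exact 95% intervals. State that the aim is descriptive if there are no non-responders.

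**Section 9.** Replace the correlation sentence with the detectable difference of the named test at the number of completers, and label the split as an assumption. For one-sided Boschloo at 20 completers, about 80% power requires these proportions improved (non-responders v responders):
- responders/non-responders 10/10: 20% v 75%, or 40% v 91%;
- responders/non-responders 15/5: 20% v 80%, or 40% v 96%.

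Either state that this also covers Aim 3 or add a separate line for it.

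**Section 5.1.** Reconcile ten and eleven per SzNET+ group, and say whether dropouts are replaced.

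**Cost.** SAP wording and a few lines of code, with no new data. The stated detectable effect becomes less favourable. The exact test also has somewhat lower nominal power than the likelihood ratio test: the median is 73% v 79% for Boschloo, over N = 20 scenarios with phi = 0.506, splits from 10/10 to 15/5 and 50–70% improving. In return, type I error is held at 5%.
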